Inhibition of Urinary Angiotensinogen and the Reduction of Blood Pressure by SGLT2 Inhibition in patients with Type 2 Diabetes

NCT Number: NCT02796170

Protocol date: 06/20/2019

Inhibition of Urinary Angiotensinogen and the Reduction of Blood Pressure by SGLT2 Inhibition in patients with Type 2 Diabetes

[name], [name]

Project Goals: Type 2 diabetes is a complex disease where hyperglycemia occurs as a result of the development of insulin resistance. It is often associated with obesity and is characterized by hyperglycemia, hyperinsulinemia, as well as hyperleptinemia. In addition to the problems associated with poor glucose control, type 2 diabetes is accompanied by a chronic inflammatory state. This chronic inflammatory state leads to a number of associated complications, including cardiovascular disease. Diabetes increases one's risk for cardiovascular disease by 2-4 fold¹, highlighting the importance of developing therapeutics that both control blood glucose levels and reduce one's risk of cardiovascular disease. The monetary impact of diabetes on our healthcare system continues to grow as well. Currently 25.8 million children and adults (8.3% of the population) in the United States suffer from diabetes². In addition to established traditional treatment options, one new approach has focused on blocking glucose reabsorption by the renal tubules to allow substantial excretion of glucose in the urine. This project will elucidate molecular and cellular mechanisms behind the potential cardio protective effects of a new class of antihyperglycemic, sodium glucose co-transporter 2 (SGLT2) inhbitors. We will also investigate clinically a potential mechanism underlying the effect of these drugs on lowering blood pressure (BP) and raising potassium (K).

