If we are unable to recruit 10 patients without hypertension we will increase the number with hypertension for a total of 30. Stratification by hypertension status will remain and is important in understanding the effect of SGLT2 inhibition in patients not on BP lowering drugs

In addition a Sulfonlyurea (SU) arm will also be included -10 patients who are on metformin and other background therapy (with the exclusion of SGLT-2 inhibitor and sulfonylurea) will be recruited. This will be an open-labeled arm. Patients will assessed at baseline. They will then receive usual care for 6 weeks. At the end of 6 weeks, patients will then undergo another assessment before being provided SU for 6 weeks. At the end of 6 weeks, patients will undergo assessment again. The aim is to determine whether any effects seen with Dapagliflozin are specific to that drug or related simply to improved glycemic control.

Inclusion criteria;

As per the current approved indications for Dapagliflozin. In addition;

- 1. Type 2 diabetes with hypertension (history of hypertension in clinical records and on medication for management of hypertension) and on RAAS blocking drugs; or
- 2. Type 2 diabetes without hypertension and not on RAAS blocking drugs
- 3. Hemoglobin A1c between 7% 10% inclusive
- 4. Background therapy for diabetes to include maximally tolerated dose of metformin.
- 5. For the dapagliflozin/placebo arm, in addition to metformin, sulfonylureas and/or insulin is allowed
- 6. Estimated glomerular filtration rate (eGFR) > = 60 ml/min
- 7. Between the ages of 18 -75
- 8. Capacity to understand and sign the informed consent.

Exclusion criteria:

- 1. Current use of Dapagliflozin or any SGLT2 inhibitor
- 2. History of intolerability to Dapagliflozin
- 3. Patients with current and past history of bladder cancer
- 4. Patients with unexplainable baseline hematuria
- 5. All current contraindications of Dapagliflozin as per the label
- 6. Severe hepatic insufficiency and/or significant abnormal liver function defined as aspartate aminotransferase (AST) >3x upper limit of normal (ULN) and/or alanine aminotransferase (ALT) >3x ULN
- 7. Total bilirubin >2.0 mg/dL (34.2 μ mol/L)
- 8. Estimated glomerular filtration rate (eGFR): <60 mL/min (calculated by Cockcroft-Gault formula)
- 9. Recent Cardiovascular Events in a patient:
- 10. Acute Coronary Syndrome (ACS) within 2 months prior to enrolment

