The IP and placebo will be labeled identically. The labels will be prepared according to Good Manufacturing Practice (GMP) and local regulatory guidelines. AZ will provide with prefilled bottles of Dapagliflozin 5 mg and the matching placebo. Labelling will be done by the sponsor.

Randomization:

The randomization code will be generated and provided by the sponsor to the site which the research site personnel will follow.

Dose and treatment regimens: After the subject has started the 5 mg dose of Dapagliflozin or the medication in test period 1, the subject will be called 1 week after initiation of study drug. If the subject is tolerating the medication, the dose will be increased to 2 tabs of placebo or 10mg of Dapagliflozin. If for some reason, the subject is not tolerating the medication the subject will continue on 5 mg daily, particularly if dizziness is present. For the sulfonylurea arm, titration of the sulfonylurea and the placebo will be at the principal investigator's discretion as per usual care. For all the patients, titration of the background medications that have the potential of causing hypoglycemia, titration of the background medications will be at the principal investigator's discretion. The purpose of titration will be to prevent hypoglycemia while the patient is in the study.

Discontinuation of IP:

The investigational drug will be discontinued according to the following criteria:

Discontinuation procedures

Patients with a central laboratory ALT and/or AST >3x ULN will be scheduled for a follow-up visit within 3 days following the receipt of the result. Patients will be discontinued from study if the initial and repeat laboratory tests meet any of the following criteria:

1. ALT and/or AST are $>3 \times$ ULN and TB $>2 \times$ ULN

2. ALT and/or AST are >5 x ULN for \ge 14 consecutive days, at any time after initial confirmatory results

3. ALT and /or AST are $> 8 \times ULN$

4. Study drug will be discontinued when eGFR is persistently $<60 \text{ ml/min}/1.73\text{m}^2$. Clinical judgement by the Principal Investigator will be used to determine if the observed decrease in eGFR $< 60 \text{ ml/min}/1.73\text{m}^2$ warrants discontinuation after the eGFR is repeated after the initial decrease in eGFR is noted.

5. Pregnancy confirmed by a positive pregnancy test or otherwise verified

Sample size calculation and statistical analysis:

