This is a pilot study. Data from this study can be used to derive the sample size for an adequately powered study. Exploratory data analysis: All data will be cleaned and logically checked.

Exploratory analysis will be conducted to examine the distributions of each variable by means of plots (bar charts, box plots, and normal probability plots) and goodness-of-fit test statistics. Means and percentages of baseline variables will be compared between the groups. Possible outliers will be detected. Data transformation will be used to normalize the distribution of continuous variables and to improve linearity in the linear regression analyses if needed.

Comparisons of continuous variables between groups will be performed using t-tests. Chi-square tests will be employed for comparisons between categorical data. Linear regression models will be fit to examine the association between a continuous dependent variables and possible independent co-variables. Data analyses will be performed using SAS version 9 (SAS Institute Inc., SAS/STAT User's Guide, Version 9. Cary, NC: SAS Institute Inc. 2007).

Patient Safety:

A copy of the MedWatch/AdEERs report will be faxed to AstraZeneca at the time the event is reported to the FDA. It will be the responsibility of the investigator to compile all necessary information and ensure that the FDA receives a report according to the FDA reporting requirement timelines and to ensure that these reports are also submitted to AstraZeneca at the same time. When reporting to AstraZeneca, a cover page will accompany the MedWatch/AdEERs form indicating the following:

- Investigator Sponsored Study (ISS)
- The investigator IND number assigned by the FDA
- The investigator's name and address
- The trial name/title and AstraZeneca ISS reference number

The collection of AEs should start after the signing of the informed consent. Investigative site will also indicate, either in the SAE report or the cover page, the causality of events in relation to all study medications and if the SAE is related to disease progression, as determined by the principal investigator. The site research personnel will send SAE report and accompanying cover page by way to AstraZeneca: [contact] or fax number is [contact].

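### Entry is set at 60 mL/min and stopping at 60 mL/min/1.73 m², so a larger patient can be eligible at a level already below the stopping threshold

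*Combined protocol and SAP*

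**What the plan says.** Three places in the protocol set a kidney-function limit.

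- Inclusion criteria, item 6: "Estimated glomerular filtration rate (eGFR) > = 60 ml/min". The unit is not indexed and no equation is named.
- Exclusion criteria, item 8: "<60 mL/min (calculated by Cockcroft-Gault formula"). The unit is again not indexed, but the equation is named.
- Discontinuation procedures, item 4: "Study drug will be discontinued when eGFR is persistently" below 60 mL/min per 1.73 m². The limit is indexed, both times it appears in the item, and no equation is named. A second sentence leaves it to the Principal Investigator whether the fall "warrants discontinuation after the eGFR is repeated after the initial decrease in eGFR is noted".

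Entry also defers to the label: "All current contraindications of Dapagliflozin as per the label" is an exclusion, and the approved indications apply. The label's renal content is not reproduced. No section converts one scale to the other, names a common equation, or limits weight or body size. On body size, the Project Goals section says of type 2 diabetes only that "It is often associated with obesity".

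**The concern.** A limit in mL/min and a limit in mL/min/1.73 m² describe the same kidney function only in a person whose BSA is 1.73 m². In a larger person, 60 on the entry scale is less than 60 on the stopping scale. Following the text as written can therefore admit someone whose value, on the scale of the stopping rule, is below the stopping level before the first tablet.

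What is at stake is consistent handling. The first sentence of item 4 is triggered by a level; the second speaks of a decrease. A patient who was low at entry and has stayed there meets the first but has nothing for the second to assess. A repeat test would confirm the value without showing that it predates treatment. Two such patients could be handled differently: one stopped for a pre-existing value, possibly losing a within-patient comparison in a 30-patient crossover, and the other continued.

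**Working it through.** The documents give no conversion or expected frequency, so there is no figure of the plan's own to reproduce.

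**Inputs from the protocol.** Entry limit 60 mL/min (inclusion item 6, exclusion item 8). Stopping limit 60 mL/min/1.73 m² (discontinuation item 4). Crossover size 30 (20 with and 10 without hypertension, Proposed Studies).

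**Assumed inputs.** All body sizes, patients and distributions below.

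**Step 1: unit conversion.** This takes the stopping value to be Cockcroft-Gault indexed to BSA.

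- Indexed value = (value in mL/min) × 1.73 / BSA
- Entry value needed to reach 60 indexed = 60 × BSA / 1.73

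| BSA (m²) | 60 mL/min, indexed | mL/min needed for 60 indexed |
|---|---|---|
| 1.5 | 69.2 | 52.0 |
| 1.73 | 60.0 | 60.0 |
| 1.9 | 54.6 | 65.9 |
| 2.0 | 51.9 | 69.4 |
| 2.2 | 47.2 | 76.3 |

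At BSA 2.0 m², entry values from 60 up to 69.4 mL/min pass entry and lie below the stopping level; at 2.2 m² the band is 60 up to 76.3. At 1.5 m² the mismatch reverses: someone between 52.0 and 60 mL/min is excluded although the indexed value is 60 or more.

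**Step 2: does it depend on the equation?** Item 4 names none, so three assumed patients aged 60 were put through several. Cockcroft-Gault = (140 − age) × weight / (72 × creatinine), × 0.85 for a woman; Mosteller BSA = √(height × weight / 3600).

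- Man, 175 cm, 100 kg, creatinine 1.5 mg/dL: 80 × 100 / (72 × 1.5) = 74.1 mL/min, eligible. BSA 2.20 m²; indexed 58.1. CKD-EPI 2021 gives 53.0 and MDRD 47.7. All are below 60.
- Woman, 163 cm, 95 kg, creatinine 1.1 mg/dL: 80 × 95 / (72 × 1.1) × 0.85 = 81.6 mL/min, eligible. BSA 2.07 m²; indexed 68.0, not below 60. CKD-EPI 2021 gives 57.5 and MDRD 50.7, both below 60.
- Man, 175 cm, 70 kg, creatinine 1.2 mg/dL: 80 × 70 / (72 × 1.2) = 64.8 mL/min, eligible. BSA 1.84 m²; indexed 60.8. CKD-EPI 2021 gives 69.2 and MDRD 61.8. None is below 60.

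The mismatch can arise under every equation tried, but whether a given patient is caught depends on the one used.

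**Step 3: how many?** Assume normal Cockcroft-Gault with mean 85 to 110 mL/min (SD 28) and normal BSA with mean 1.95 to 2.1 m² (SD 0.2). Share affected = proportion with Cockcroft-Gault × 1.73 / BSA < 60 among those with Cockcroft-Gault ≥ 60. Weight enters both quantities, so a positive correlation is expected and was varied.

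| Assumed correlation | Lowest (means 110, 1.95) | Highest (means 85, 2.1) |
|---|---|---|
| 0 | 3.6% | 18.6% |
| 0.3 | 2.3% | 17.2% |
| 0.5 | 1.5% | 16.0% |
| 0.7 | 0.7% | 14.6% |

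Out of 30 patients, the extremes are 30 × 0.007 = 0.2 and 30 × 0.186 = 5.6.

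**The case against.** The strongest reply is that item 4 already handles such a patient. It requires a persistent value and a repeat, and asks the investigator to judge a decrease. This largely stands against three stronger conclusions that a reader might draw.

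- *That the patient must be stopped.* The text does not say so; the decision is left to judgement after the repeat.
- *That continuing would breach the protocol.* It need not, for the same reason.
- *That the rule takes no account of change on treatment.* Its second sentence is framed around a decrease, and Visit 2 includes a blood draw. What is missing is a baseline on the rule's own scale and a statement of how the level and the decrease fit together.

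It can also be said that something else at entry closes the gap. Inclusion item 6 names no equation and might be applied with the same eGFR as item 4, although its unit speaks against that. The label might set its own renal limit, but its content is not given. Either could help in practice; neither is shown in the documents, and both would leave exclusion item 8 at odds with item 4.

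Finally, the loss of data is limited. In the dapagliflozin/placebo schedule, the visits within each treatment period are telephone calls, and scheduled on-treatment blood draws come at its end (Visits 6 and 12). A low value at Visit 12 costs no pair. Losing one needs a stop prompted by the baseline, Visit 6 or Visit 8 draw, or an unscheduled one, followed by a confirming repeat and a decision to stop. This stands: lost pairs would be fewer than the patients caught by the mismatch.

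**Conclusion.** The inconsistency holds. The entry and stopping limits share a number but not a scale, and the text does not reconcile them. A larger patient can be eligible while already below the stopping level, and item 4 leaves unclear what then applies.

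The size is conditional. The figures of 51.9 and 47.2 are exact only if the stopping eGFR is Cockcroft-Gault indexed to BSA. The share of roughly 1–19% rests wholly on assumed means, SDs and correlation, so a reader should not take it as an expected count in this trial: the low end is under one patient in 30. The contradiction does not depend on that share. It is a consistency fault in a written safety rule, worth correcting because correction is cheap; it does not by itself undermine the primary comparison.

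**What to change.** Reconcile the entry criteria with the discontinuation procedures: state one equation and one unit, and use them in inclusion item 6, exclusion item 8 and discontinuation item 4. Record each patient's pre-treatment value on that scale, so that an on-study value is compared with it, and say in item 4 how the rule applies to a value that was already low before treatment. Which equation, unit and threshold to use is for the sponsor and investigator to decide.

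The cost is a short amendment. Creatinine, age, sex, height and weight are routine, and the Visit 2 blood draw could supply the baseline; if serum creatinine is not already run on it, that is one added assay. The downside is that a few borderline patients may change eligibility, in either direction depending on body size and the choice made.

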Serious adverse events that do not require expedited reporting to the FDA will be reported to AstraZeneca preferably using the MedDRA coding language for serious adverse events. In the case of blinded trials, AstraZeneca will request that the Sponsor either provide a copy of the randomization code/ code break information or unblind those SAEs which require expedited reporting. All SAEs have to be reported to AstraZeneca, whether or not considered causally related to the investigational product. All SAEs will be documented. The investigator is responsible for informing the IRB and/or the Regulatory Authority of the SAE as per local requirements.

Visit Schedule:

Following is the schedule of the study visits:

- 1. Visit 1(screening visit): Screening and informed consent will be conducted during this visit. If subjects meet the inclusion criteria they will come back within 4 weeks for randomization. If the required laboratory tests to establish whether the subject meets the inclusion criteria are available and have been drawn within the past ninety days, no laboratory tests will be required at this visit. However, if not, laboratory tests will be drawn at this visit for the purpose of establishing that the subject meets the criteria for inclusion in the study. The patient will be asked to keep a log of the blood sugars while participating in the study.
- 2. Visit 2 (baseline visit): During this fasting baseline visit, subject will undergo history and physical, blood draw, urine sample, EndoPAT test and given a bottle for 24 hour urine collection. Subjects will

be given the monitor for 24 hr. BP monitoring. The patient will return the monitor along with a 24 hour urine sample

If however during the screening visit, the laboratory results are available for review and the patient qualifies for the study, the screening and the baseline visits will be combined.

- 3. Visit 3 (randomization visit) subject will return the ABPM monitor and urine bottle and will be randomized to either dapagliflozin or placebo in a double-blind fashion. The first arm of the study will be labeled test period 1 and the second arm of the study will be labeled test period 2. All subjects will be educated on the recognition and management of hypoglycemia at this visit.
- 4. Test period 1: Test period 1 will start once the subject has taken the first dose of the drug to which the subject was randomized. Test period 1 will continue for 6 weeks.

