- 5. Visit 4 (Telephone visit). After the subject has started the 5 mg dose of the medication in test period 1, the subject will be called 1 week after initiation of study drug. If the subject is tolerating the medication, the dose will be increased to 2 tabs (10mg). If for some reason, the subject is not tolerating the medication the subject will continue on 5 mg daily, particularly if dizziness is present. The patients will also be asked if they have had any low blood sugars and what time the low blood sugars were. The blood sugars will be relayed to the PI in case there is any hypoglycemia. The PI will then make the necessary changes to the patient's background therapy to prevent further hypoglycemia.
- 6. Visit 5 (telephone visit): Visit 5 will be a telephone visit that will occur 2 weeks after the visit 4 telephone visit. The purpose of the telephone visit is to ensure that the subject is tolerating the medication. This is particularly important if the dose had been increased to the maximum dose of 2 tablets during visit 4. The patients will also be asked if they have had any low blood sugars and what time the low blood sugars were. The blood sugars will be relayed to the PI in case there is any hypoglycemia. The PI will then make the necessary changes to the patient's background therapy to prevent further hypoglycemia.
- 7. Visit 6 (cross over visit) –Visit 6 will occur 6 weeks +/- 7 days after randomization. The subject will come in fasting for this visit. During this visit, subject will undergo a brief physical examination. Blood and urine sample will be collected and the EndoPAT procedure will be conducted. Subject will take the last dose of the first lot of medication on the day of visit 6. Subject will start the24 hr. AMBP and 24 hour urine collection on the day of visit 6 after taking the last dose of the medication for test period 1.
- 8. **Visit 7**: Next day. Return AMBP monitor and then start the washout period which will last at least 14-28 days.
- 9. Test period 2: Test period 2 will start with visit 8
- 10. Visit 8: After the washout period of 14-28 days, the subject will come to the research suite in a fasting state and undergo blood and urine sample collection. Patient will receive the second medication and enter test period 2. The subject will start the new lot of medication- dapagliflozin at 5 mg (1 tablet) or placebo. During this visit, the subject will undergo EndoPAT procedure and will be started on ABPM.

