- 11. Visit 9 (the day after visit 8): The subject will return the ABPM.
- 12. Visit 10 (telephone visit): After the subject has started the medication in test period 2, the subject will be called 1 week later. If the subject is tolerating the medication, the dose will be increased to 2 tablets daily (10 mg). If for some reason, the subject is not tolerating the medication the subject will continue on 5 mg daily, particularly if dizziness is present. The patients will also be asked if they have had any low blood sugars and what time the low blood sugars were. The blood sugars will be relayed to the PI in case there is any hypoglycemia. The PI will then make the necessary changes to the patient's background therapy to prevent further hypoglycemia.
- 13. Visit 11 (telephone visit): will be a telephone visit that will occur 2 weeks after visit 10 which is also a telephone visit. The purpose of the telephone visit is to ensure that the subject is tolerating the medication. This is particularly important if the dose had been increased to the maximum dose of 2 tablets (10 mg) during visit 7. The patients will also be asked if they have had any low blood sugars and what time the low blood sugars were. The blood sugars will be relayed to the PI in case there is any hypoglycemia. The PI will then make the necessary changes to the patient's background therapy to prevent further hypoglycemia.
- 14. Visit 12; (end of treatment visit): This visit will conclude test period 2 six weeks after the washout period. During this fasting visit, a brief physical examination will be done, blood and urine samples will be collected, and the EndoPAT procedure will be conducted. Subjects will take the last dose of the second lot of medication on the day of visit 11. Subject will start the 24 hr. AMBP and urine collection after taking the last dose of the medication for test period 2.
- 15. Visit 13: The day after visit 12, the subject will return the AMBP monitor. This concludes the study.

NOTE: In order to give patients flexibility all visit will have a window of +/-7 days for visits **Study Flow chart:**

A: For the study comparing Dapagliflozin and placebo:

Visit 12 (cross over visit- 6 weeks +/- 7 days after visit 8)

- 5- physical examination
- 6- Fasting laboratory work up

(Collection of fasting blood and urine samples)

- 7- Subject is started on ABPM. Subject takes the last dose of the medication given in test period 2
- 8- EndoPAT procedure conducted.

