Visit 13 (the day after visit 12)

Subject returns the ABPM and 24 hour urine collection No physical exam No blood or urine collection

Protocol for the sulfonylurea arm:

Visit 7 (the day after visit 6) Subject returns the ABPM and urine No physical exam No blood or urine collection

Visit 12 (the day after visit 11)

Subject returns the ABPM and 24 hour urine collection No physical exam No blood or urine collection

Measurements:

- 1- Blood pressure will be measured as per clinical practice and we will also do a 24 hr. ambulatory blood pressure monitoring before and after 6 weeks of treatment in the Dapagliflozin/ placebo arm as well as before and 6 weeks after treatment in the Sulfonylurea/placebo arm
- 2- We will also measure vascular compliance/ endothelial function using the EndoPAT test at the same visits as the ABPM only in the Dapagliflozin/placebo arm.
- 3- Spot and 24 hour urine will be collected. Urine samples will be obtained, before and after treatment. After appropriate processing, the samples will be quickly stored at -20°C, and analyzed for concentrations of AGT, albumin, and creatinine within one week of collection as previously described. The urinary AGT concentrations and urinary albumin concentrations will be normalized by urinary creatinine concentrations. Urine creatinine will also be measured and urine AGT/ creatinine calculated to correct the AGT for volume of excretion. Plasma K, renin and AGT will be measured at these visits.
- 4- Fasting plasma glucose will be measured for the Dapagliflozin/placebo and sulfonylurea arm at the following time points: a) at baseline and end of period 1 and b) at baseline and end of period 2.

Blood and urine will be stored at -70°C, for future testing of other biomarkers of renal and cardiovascular disease.

Measurements	Timings
ABPM and 24 hour urine collection	 Dapagliflozin/Placebo arm Before randomization visit (in test period 1) At the end of test period 1 (before entering washout period) At the beginning of test period 2 At the end of test period 2 (at the end of the study)
	Sulfonylurea arm - Before usual care arm visit (ie visit 2 in test period 1)

The table below summarizes the timings of the measurements:

	 At the end of test period 1 At the end of test period 2 (at the end of the study) 		

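### As the visit text is written, the period-2 baseline 24-hour ABPM starts at the same visit as the period-2 drug, while the period-1 baseline is wholly pre-drug

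*Combined protocol and SAP*

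**What the plan says.** **Period 1** (Visit Schedule, Visits 2 and 3). The monitor and urine bottle are issued at Visit 2. At Visit 3 the "subject will return the ABPM monitor and urine bottle and will be randomized to either dapagliflozin or placebo in a double-blind fashion". The next item adds: "Test period 1 will start once the subject has taken the first dose of the drug to which the subject was randomized".

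**Period 2** (Visit Schedule, Test period 2 and Visits 8 and 9). "Test period 2 will start with visit 8". The Visit 8 entry lists fasting blood and urine samples first. It continues "Patient will receive the second medication and enter test period 2", then "The subject will start the new lot of medication- dapagliflozin at 5 mg (1 tablet) or placebo", then "During this visit, the subject will undergo EndoPAT procedure and will be started on ABPM". The next entry is "Visit 9 (the day after visit 8): The subject will return the ABPM".

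**Measurements.** Item 1 describes ABPM in the dapagliflozin/placebo arm as done ahead of and following six weeks of treatment, and item 3 says the same of urine in general terms. The timings table schedules ABPM and 24-hour urine "At the beginning of test period 2". The Visit 8 and Visit 9 entries do not mention the 24-hour urine.

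**The concern.** A baseline recording should end before the first dose of the period it serves. The period-1 recording does. The period-2 recording, on the literal visit text, runs over the first day of dosing.

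The asymmetry matters in one sequence only. Patients on placebo in period 2 take nothing active during the recording. Patients who receive dapagliflozin second may have drug on board in their baseline, so the same treatment would be measured against two different starting conditions. Any first-day effect in the direction of the six-week effect would shrink the change seen in that sequence.

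The quantities at stake are changes. Hypothesis 1 pairs urine AGT with ABPM, Hypothesis 2 links AGT reduction to BP reduction, and exploratory endpoint 2 uses change in BP. The primary endpoint compares urine AGT before and after treatment, so it could be touched if the 24-hour collection supplies the value; the protocol does not say whether spot or 24-hour urine is used.

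**Working it through.** The plan states no figure on this point, so there is none to reproduce. The check is the order of events, followed by simple arithmetic on the overlap.

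**1. Order of events**

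| | Period 1 | Period 2 |
|---|---|---|
| Monitor on | Visit 2 | Visit 8 |
| Drug start in the visit text | after randomisation at Visit 3 | listed under Visit 8 |
| Monitor off | Visit 3, with randomisation | Visit 9, the next day |
| Overlap with drug | none | possible, up to about 24 hours |

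Two details support reading Visit 8 as the dosing day. The flow chart times Visit 12 at six weeks from Visit 8, just as Visit 6 is timed six weeks from randomisation. And at Visits 6 and 12 the text says that ABPM begins after the dose, whereas Visit 8 gives no order.

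**2. Share of the recording on drug.** For a tablet taken x hours after the monitor starts, share = (24 − x)/24. The times are assumed:
- x = 0: 24/24 = 100%
- x = 6: 18/24 = 75%
- x = 12: 12/24 = 50%
- tablet held to Visit 9: 0%

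**3. Patients exposed.** Number = p × 30, where p is the share receiving dapagliflozin second (not stated):
- p = 1/3: 10
- p = 1/2: 15
- p = 2/3: 20

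**4. Effect on a mean change.** Let f be the share of the six-week BP effect already present in the period-2 baseline recording. The documents give no first-day effect, so every f is an assumption. The period-2 dapagliflozin change keeps 1 − f of its true value. The average over both sequences keeps 1 − p·f. With p = 1/2:

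| f | Period-2 change kept | Average kept |
|---|---|---|
| 0 | 1.00 | 1.00 |
| 0.10 | 0.90 | 0.95 |
| 0.25 | 0.75 | 0.875 |
| 0.50 | 0.50 | 0.75 |

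This shows the mechanism and does not estimate the bias. The recording covers one day at the 5 mg starting dose, so f may be near zero.

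**5. What is and is not reached.** Reached: change from the period-2 ABPM baseline, and change from a period-2 24-hour urine baseline if that collection runs alongside the monitor. Not reached: end-of-period comparisons, patients on placebo in period 2, and spot urine AGT and fasting blood at Visit 8, both listed ahead of the drug. No claim is made about EndoPAT.

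**The case against.** **The flow chart may settle it.** The boxes for Visits 8 and 9 are not in the text available here. That stands as a limit on certainty. It does not change what the Visit 8 entry says, and a site working from that entry could dose that day.

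**A period's start need not mean a dose.** The timings table labels the pre-randomisation ABPM as belonging to test period 1, so the beginning of period 2 could equally mean a pre-drug baseline. This weakens any inference from the period definitions alone. But the Visit 8 entry also says that the new medication is started, and that does not depend on how a period is defined.

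**A pre-treatment baseline was clearly intended.** Measurements items 1 and 3 show it. Agreed; the visit text does not secure that intention.

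**Little depends on it.** Mean ABPM change is not a listed endpoint. Hypothesis 2 and exploratory endpoint 2 refer to BP without naming ABPM, and clinic BP is also measured. This is a pilot that claims no power. All of this stands and is why the point is minor.

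**Stronger readings.** A reader might infer that the BP–AGT association would be weakened by a known amount. The documents do not support that. A slope of BP change on AGT change would be multiplied by 1 − p·f only if the AGT change were unaffected. If both changes shrank by the same f, without noise, with p = 1/2, correlation 0.5 and mean/SD of 1 for each, the slope ratio would be about 1.003 at f = 0.10 and 1.02 at f = 0.25: no loss. A reader might also infer that the primary endpoint is biased. That would require 24-hour urine to be the specimen used and to be collected with the monitor, and neither is stated.

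**Conclusion.** The point holds as a minor weakness in the Visit 8 text. Followed as written, up to about 24 hours of the period-2 baseline ABPM, and of any 24-hour urine collected with it, can fall on drug in patients receiving dapagliflozin second. The period-1 baseline is wholly pre-drug.

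The conclusion rests on the visit entries alone. It assumes that the tablet is taken on the day of Visit 8 and that the missing flow-chart boxes do not say otherwise. The documents do not show that patients were in fact dosed during the recording. The size of any bias cannot be derived and may be small, and no mmHg figure is claimed. The case for changing the text is that the asymmetry can be removed almost for free.

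**What to change.** - **Visit 8:** take the fasting samples, do EndoPAT, issue the monitor and the 24-hour urine bottle, and dispense the drug with an instruction not to start it.
- **Visit 9:** take the first period-2 tablet after monitor and bottle are returned, mirroring Visits 2 and 3. List the 24-hour urine in the Visit 8 and 9 entries.
- **Visit 12:** time it six weeks from Visit 9.
- **Analysis text:** state that only values collected before the first dose of a period count as its baseline.

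**Cost.** Period-2 dosing starts one day later, within the ±7 day window, with no added visit because the patient already attends Visit 9. The drug-free gap grows by one day and stays within 14 to 28 days if Visit 8 falls by day 27 of the washout. If Visit 12 were left six weeks from Visit 8, period-2 dosing would be 42 − 1 = 41 days, which is why it should move too.
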